5.2. Rationale

Currently, children with linear growth failure are identified *ad hoc*, if at all, because there is no systematic screening programme in the UK. Several other European countries systematically monitor linear growth in pre-school children, resulting in earlier diagnosis of medical causes of short stature.¹⁴ From parent testimonials, it is apparent that there are often delays in identifying serious medical disorders such as growth hormone deficiency. Developing a screening algorithm for the UK pre-school population would be a major step towards identifying growth failure earlier.

Early identification leads to prompt and appropriate investigation, identification of potential co-morbidities and improves prognosis. Timely initiation of appropriate therapy is critical to minimise the impact of the disease process and maximise general health as well as height gain. Stunting is a sensitive marker of a child's wellbeing, health and educational potential across the life-course. If we generate pilot data

suggesting that growth and development measures in early childhood both improves the early identification of vulnerable children and increases the sensitivity of detecting poor school readiness, it will provide a strong rationale for a new public health approach to identifying vulnerable children in need of pre-school support through simple measurements. Using our algorithm, the screening process would be automated and have potential for adoption at scale.

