6.2. Secondary objective

Generate pilot data to investigate the best indicators to detect poor school readiness and/or developmental problems in early childhood.

Within the secondary objective we aim to test the following two hypotheses:

- 1. The addition of growth and development data to other environmental and socioeconomic variables (including Index of Multiple Deprivation) increases the pick-up rate of children at risk of poor school readiness and/or children with delayed development.
- 2. There is strong correlation between the existing measurement of child development in pre-school age children (ASQ-3) and a gold standard developmental assessment by a child psychologist.

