We will employ an algorithm based on previous methodology, using variables individually and in combination, after checking for co-linearity. Different cut-off values will be chosen and the proportion of the population judged to have linear growth failure estimated for each cut-off. We will then examine the detection rate for each cut-off by applying it to data from ~200 local children treated in the specialist paediatric endocrinology centre with known growth disorders e.g. Growth Hormone Deficiency (GHD), Turner Syndrome (TS) and Small for Gestational Age without catch-up growth (SGA). Consent will be obtained retrospectively from these patients and their parents/carers to link their routinely obtained clinical data (diagnosis, age at diagnosis, height and parental height) to previously height data obtained at school entry via the NCMP. To do this linkage, the hospital clinical data (and the associated NHS number or other identifiers) will be shared with NHS England. This will allow us to calculate sensitivity-and-specificity algorithm cut-offs for the detection of these conditions. This will enable a trade-off between detection rate (sensitivity) and the false positive rate (1-specificity) to be evaluated. Additionally, the time elapsed from the first abnormal screening result until the clinical diagnosis of growth hormone deficiency will be related to the cut-off values.

The outcomes for Aim 1 are age of identification of stunting (which will be reported but the study is not powered to detect age of diagnosis); feasibility of measuring children in the community; the percentage of children referred; the percentage of children found to have underlying medical conditions; and the feasibility, acceptability and inter-test variability of a smartphone app and stadiometer height measures.

The algorithm will be applied to measures collected from each child at each visit, with children who are identified by the algorithm as being in the bottom 2% for height or

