growth being referred to clinic for further investigation. The proportion of children with complete observations, including height at three time points and parental height, will be compared to the proportion of children with fewer observation points or missing parental height. Descriptive statistics will be reported: the number and percentage of children found to be stunted and their characteristics (height, gender, age, socio-demographic factors). We will also report the number of children referred to clinic, attending clinic and found to have underlying medical conditions. The age at which each condition is identified will be reported and compared to the average age at diagnosis.

Height data collected by parents using a smartphone app will be analysed. The number of parents consenting to use of the smartphone app and reporting one or more height measurements through the app will be reported. The number of time points at which parent's upload smartphone measured heights will also be reported. Inter-rater reliability between parent-measured height using the smartphone app and Health Visitor measured height using a stadiometer will be assessed using Gwet's Agreement Coefficient.¹⁹

Aim 2

All children will undergo a developmental assessment in the community, conducted by a health visitor with input from the child's parent, as part of standard care (ASQ-3 questionnaire). A subset of 150 children will, in addition, have a gold standard developmental assessment conducted by a child psychologist using the GMDS, which measures gross motor, fine motor, social, language, visual-spatial and practical reasoning skills.

Data on socioeconomic circumstances will be used to model the probability of a child's risk of developmental delay or sub-threshold delay on the ASQ-3 (n=600) and GMDS (n=150). Poor growth (assessed by the algorithm) will then be included in these models to assess whether model fit is improved, and whether poor growth contributes to the predictive power of socioeconomic variables to predict developmental delay.

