Concurrent validity of the ASQ-3 and GMDS will be assessed. Each measure will be used to assess whether the participant has any degree of developmental delay, based on measure-dependent cut offs. The degree of agreement will be assessed using Cohen's kappa, and interpreted using existing guidelines, where a kappa value of >0.4 reflects moderate agreement, and a kappa of >0.6 reflects substantial agreement.²⁰ The GMDS will also be used as a gold standard child development measure to assess the performance of the ASQ-3. Sensitivity and specificity will be calculated to assess the ability of the ASQ-3 of identifying children identified as having a delay by the GMDS.

The outcomes for Aim 2 are the correlation between the ASQ-3 and the GMDS; and the change in sensitivity with the addition of anthropometric and developmental data to an existing vulnerability index.

Qualitative analyses

To further our understanding of the acceptability of the proposed screening programme, we will conduct two focus groups with parents participating in the study, as well as one focus group with health visitors. The transcribed data from the focus groups with caregivers and health visitors will be used to generate coding categories and will be analysed using NVivo, using thematic analysis.

11. Ethics

Research Ethics Committee approval will be sought. This is not a trial and there is no intervention which could result in direct harm to participants. However, there are potential indirect harms related to the study. We will aim to mitigate these as far as possible and will include detail of these potential harms in the patient information and informed consent procedures.

Firstly, the study will involve collecting sensitive data, which if handled incorrectly could lead to identification of individual children or groups of children. The study procedures to de-identify or pseudo-anonymise children will reduce the risk of identification of individuals. The potential for 'group harm', in which a particular subpopulation (e.g. by area, ethnicity or gender) are stigmatized because of study findings, such as the finding of high prevalence of growth failure, will be minimized in publications and dissemination of study findings, by not releasing results relating to small areas.

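### The Aim 2 added-data outcome is a change in sensitivity alone, so a gain can come from flagging more children; its comparator also differs from that of the described models

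*Protocol*

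**What the plan says.** Three places in the protocol describe the Aim 2 added-data question, all in terms of detection only.

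- Section 6.2, hypothesis 1: adding growth and development data to environmental and socioeconomic variables "increases the pick-up rate of children at risk of poor school readiness and/or children with delayed development".
- Section 5.2: the rationale looks for pilot data showing that such measures improve early identification and that their use "increases the sensitivity of detecting poor school readiness".
- Section 10.2, end of Aim 2: the declared outcome is "the change in sensitivity with the addition of anthropometric and developmental data to an existing vulnerability index".

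The analysis paragraph in 10.2 is framed differently. Socioeconomic data are used to model the probability of "developmental delay or sub-threshold delay on the ASQ-3 (n=600) and GMDS (n=150"). Then "Poor growth (assessed by the algorithm) will then be included in these models to assess whether model fit is improved", and also "whether poor growth contributes to the predictive power of socioeconomic variables to predict developmental delay".

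Specificity appears in 10.2 for two other comparisons. For the Aim 1 cut-offs the plan evaluates the "trade-off between detection rate (sensitivity) and the false positive rate (1-specificity"). For ASQ-3 against GMDS, "Sensitivity and specificity will be calculated to assess the ability of the ASQ-3". The added-data comparison has no such counterpart.

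**The concern.** Sensitivity read alone does not separate a better marker from a looser rule. If the enlarged model or index flags more children than the base one, it will tend to find more true cases whether or not the added variable is related to delay. The cost is more children flagged without delay, and the declared outcome does not record it.

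This matters because section 5.2 would use such a result as support for a new public health approach to targeting pre-school help. Section 11 also recognises that being identified with poor growth or delayed development can cause distress and stigma, so false positives have a cost.

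A second difficulty is that the declared outcome and the described models do not share a starting point or the same added data. As written, the models would not produce the outcome.

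**Working it through.** The protocol gives no base sensitivity, threshold, flagged share or target gain for this comparison, so there is no stated figure to reproduce. The calculations below show direction and rough size under stated assumptions.

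**1. Growth added as an extra flag (a rule the protocol does not state).** Let s be base sensitivity, sp base specificity, and f the share flagged by a marker unrelated to delay. A child counts as positive on either flag.

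- New sensitivity = s + (1 − s)f
- New specificity = sp(1 − f)

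The value f = 2% is borrowed from the Aim 1 referral share in 10.1 and 10.2; s and sp are assumed.

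- s = 0.40: 0.40 + 0.60 × 0.02 = 0.412, a gain of 1.2 points.
- s from 0.30 to 0.70: gain from 0.70 × 0.02 = 1.4 points down to 0.30 × 0.02 = 0.6 points.
- sp = 0.90: 0.90 × 0.98 = 0.882, a loss of 1.8 points.

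Under this rule sensitivity cannot fall, but a rise in a given sample is not certain. With k missed cases, the chance that the noise flag catches at least one is 1 − 0.98^k. Assume s = 0.40 and delay in 10–15% of children.

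- n=600: k = 36 to 54, chance about 52% to 66%.
- n=150: k = 9 to 13.5, chance about 17% to 24%.

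**2. Growth added to a nested model, as 10.2 describes.** Logistic models were simulated 2,000 times per setting. The assumptions were about 14% with delay, one real base predictor with log-odds ratio 0.7 per SD, and added predictors that are pure noise. Sensitivity was measured on the children used for fitting. Cells give the mean change in sensitivity in percentage points, then the share of runs in which it rose / fell.

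| n | Noise terms | Threshold at observed prevalence | Threshold 0.20 | Top 15% flagged in both models |
|---|---|---|---|---|
| 600 | 1 | +0.2; 37% / 30% | +0.6; 42% / 25% | +0.3; 36% / 29% |
| 600 | 5 | +1.2; 56% / 31% | +3.2; 73% / 16% | +1.6; 61% / 24% |
| 150 | 1 | +0.9; 32% / 23% | +2.5; 38% / 16% | +1.3; 34% / 20% |
| 150 | 5 | +4.4; 58% / 20% | +10.6; 76% / 9% | +6.3; 65% / 15% |

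Noise moves sensitivity in both directions, with a lean towards a gain that grows with fewer children and more terms. The last column shows that holding the flagged share fixed does not remove in-sample optimism. In the same simulations a 5% likelihood-ratio test favoured the noise terms in only 5–6% of runs.

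**3. Comparator, side by side (both in 10.2, Aim 2).**

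| | Analysis paragraph | Declared outcome |
|---|---|---|
| Starting point | Socioeconomic variables | A vulnerability index, not defined in the protocol text |
| Added | Poor growth from the algorithm | Anthropometric and developmental data |
| Measure | Model fit, predictive power | Change in sensitivity |

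The two descriptions differ in every row.

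**The case against.** A reader might infer that adding any data, even noise, must raise the outcome, so that hypothesis 1 can hardly fail. The protocol does not support that. It needs the either-flag rule, which is stated nowhere. In the nested models that are described, one noise term at n=600 lowered sensitivity in 25–30% of runs at a fixed probability threshold. The fit and predictive-power criteria can also fail: raw likelihood always improves with an added term, but a formal test rejects noise at about its nominal rate. Large spurious gains would need flagged shares well above the 2% or 2–3% that the protocol mentions, or many more terms than the single growth term in the models.

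A reader might also infer circularity, since ASQ-3 is both a developmental measure and the modelled outcome at n=600. The protocol does not say that the same ASQ-3 score would stand on both sides, and it plans a repeat ASQ-3 at follow-up.

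It is also fair to say that thresholds, the choice of test and internal validation commonly belong in a statistical analysis plan, which was not available here, and that Aim 2 is a secondary objective meant to generate pilot data, with no success threshold. This lowers the weight of the point. It does not remove it, because the sensitivity-only outcome and the differing comparator are fixed in the protocol text.

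**Conclusion.** The concern holds in a limited form. The declared outcome for Aim 2 hypothesis 1 cannot by itself show that growth carries information, because a gain can come simply from flagging more children, and it is not the quantity that the described models yield.

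The likely distortion is modest for one growth term at n=600: 0.2 to 0.6 points on average in the nested models, or 0.6 to 1.4 points with an unrelated 2% extra flag. It is larger at n=150 or with several added terms, up to about 10.6 points in the least favourable setting simulated. These sizes rest on the assumed prevalence, base sensitivity, predictor strength and thresholds. The gap in the outcome definition and the comparator mismatch do not depend on them. Severity is moderate.

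**What to change.** In 10.2, redefine the outcome as the paired change in sensitivity between the socioeconomic base model and the same model plus growth data, in the same children, at the same proportion flagged. The proportion flagged by the base model is a natural choice. If the proportion is not held fixed, report the change in specificity beside it. When it is fixed, specificity adds nothing: with prevalence p, the change in specificity equals p/(1 − p) times the change in sensitivity.

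Give a bootstrap 95% confidence interval with optimism correction, since fixing the proportion flagged leaves the in-sample gain in place. Use this one base comparator in both the analysis paragraph and the outcome statement.

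The cost is a wording change and a little more programming, with no new data. The downside for the sponsor is that the reported gain will probably be smaller.

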11.1. Annual Safety Reporting

N/A

12. Public involvement

The screening algorithm will be created using national data and piloted for feasibility and acceptability in east London, which we have shown is a national hotspot for stunting based on an analysis of NCMP data (currently in review). We have engaged with **the Patients Association**, an independent national charity which campaigns for improvements in health and social care for patients, who stated in a letter to us that in order "to ensure an effective co-production approach to this research bid we welcome the opportunity to work in partnership with Queen Mary, University of London and other local stakeholders to undertake research into child malnutrition which will build on the work we have previously undertaken in 2016/2017."

The **Child Growth Foundation (CGF)** have identified this area of research as one of their key missions / research priorities and provided a letter of support for this work. As Medical Advisor for the CGF, [name] will disseminate and obtain feedback from CGF members via their website, newsletters and annual congress. The CGF are also able to provide individuals for a project advisory board, focus groups and workshops.

As per Section 9.4, we will also engage groups of caregivers in focus groups to develop our understanding of caregivers' experience and understanding of child growth and development, and their thoughts about the current processes for monitoring of these metrics in Tower Hamlets.

13. Data handling and record keeping

13.1. Data management

During Aim 1, we will collect sensitive clinical data including height, weight, developmental information and carer-recalled past medical history. We will also collect sensitive sociodemographic information including data on household deprivation and other social determinants of health. Data from anthropometric assessments, developmental assessments and questionnaires will be entered onto a secure password protected access database (REDCap), and the hard copies of the questionnaires will be stored centrally in a locked cupboard. Two health visitors will double enter the data and resolve any discrepancies.

All data will be linked to an identifier kept separate from the sensitive data. No copies of paper documents will be made. Data will be identifiable only by a unique study ID number and will not display participant identifiable information. A linkage form will be used to link study ID with patient identifiable information (pseudo-anonymisation), which will be stored as a password-protected file on a locked QMUL computer.

The smartphone app we will invite caregivers to use converts height data from the camera image to a numerical figure, and this will be transferred to a secure central server with additional relevant demographic data (e.g. gender, ethnicity, weight, date of birth and parents' heights) and an anonymous identifier in GDPR-approved secure space. Each patient will have an anonymised unique identifier. No patient images / names will be transferred.

Research staff will undergo Good Clinical Practice and ethics training and the importance of confidentiality when reviewing sensitive clinical documents will be emphasised throughout the study. Child development assessments are potentially sensitive, because they measure cognitive performance, and can be misinterpreted or could be used to disadvantage a child. The results will be discussed in confidence with caregivers; we would seek their permission before sharing any of these findings and would only do so if it were in the best interests of child, for example to inform an Education Health and Care Plan to seek additional educational support for the child.

Linkage of the children's data we collect with the pseudo-anonymised national data will contain information such as postcode. Although not a direct identifier, this could lead to identification of groups of children. The potential for 'group harm', in which a particular subpopulation (e.g. by area, ethnicity or gender) are stigmatized because of study findings, such as the finding of high prevalence of growth failure, will be minimized in publications and dissemination of study findings, by not releasing results relating to small areas.

We will also conduct a linkage exercise of previously collected routine clinical data to historic height measurements. Retrospective consent will be sought from patients and parents or carers of a sample of patients who received treatment for growth-related conditions at [name] paediatric endocrinology clinic at Barts Health NHS Trust. Data on the child's diagnosis, age at diagnosis and parental heights, as well as their NHS number and other identifiers, will be shared with NHS England. NHS England will link these data, using the NHS number, or other identifiers when the NHS number is not available in the NCMP dataset, to the child's first NCMP height measurement, as well as the age of the child when the measurement was taken in months. These data will then be anonymised by removing the NHS number or other identifiers and a new randomly generated identifier assigned to each child. Finally, this pseudo-anonymised dataset will be shared with the Office for Health Improvements and Disparities (OHID), part of the Department of Health and Social Care. Data will be analysed at OHID according to an analysis strategy developed at QMUL, to minimize data sharing. OHID has robust data protection protocols and safe and encrypted sharing pathways with NHS England.

13.1. Source Data

Source data include the anthropometric measurements and developmental assessments and sociodemographic data collected from children and their carers in the community. From experience, it is expected that most children will be brought to their appointment by at least one parent. In this case, the child's parent will also have their height measured, and will be asked about the height of the other parent. We will not apply for approval to access the medical notes of either the child or of the carers/parents, especially since heights entered in medical notes are often recorded from a verbal report from the patient given to the clinician coding the measurement, rather than a direct measurement.

13.2. Confidentiality

Information related to participants will be kept confidential and managed in accordance with the Data Protection Act, the General Data Protection Regulation (GDPR), NHS Caldecott Principles, the UK Policy Framework for Health and Social Care Research, and the conditions of Research Ethics Committee favourable opinion.

13.3. Record retention and archiving

We will keep research records for 20 years after the project has completed, as per the UK Policy Framework for Health and Social Care Research. We will use the Trust Corporate Records Centre as the repository for long-term storage. All research documentation will be archived in physical form.

14. Safety reporting

Given the study design, we do not anticipate adverse events (AE) or adverse reactions (AR). Adverse events could plausibly occur during the face-to-face components of the study. There are two points at which participants will be seen face-to-face. One at age 2-2.5 years, where an anthropometric assessment and developmental assessment will take place on the same day, and an almost identical assessment between 6-12 months later at the GP surgery. The third measurement will take place at the child's school as part of the NCMP, and any children seen in the paediatric endocrinology clinic by [name] will be receiving normal clinical practice. The NCMP measurement and the clinic appointment are not strictly part of the study procedures. There is a very low likelihood of physical injury during the growth and development assessments and/or while the child and caregiver are on the premises.

The research nurses will make an initial assessment of any injury and will seek medical attention as appropriate.

Other contacts will be with the families of children who warrant referral to a paediatric clinical service, which will be in the form of a telephone call and/or letter to the family and to the child's GP. There is potential for distress or psychological harm of the child or family member when being informed of abnormal growth or development or when being referred to the growth clinic. This will be minimized by the breaking of news or discussion of clinical information being undertaken by a senior medically trained member of the research team with advanced training in communication skills.

Any AEs that are plausibly related to the study and which are identified by a member of the research team (including research nurses, psychologist, health visitors or any of the study co-investigators) will be reported to the study CI. The CI or another medically qualified research team member will assess each identified AE for severity and relatedness to establish if it should be classified as a serious adverse event (SAE) and whether the event was related to the study. The assessment will be documented in the participant's study records. The CI or delegate will report any severe AEs or SAEs that are possibly, probably or definitely related to study procedures to the JRMO; a safety reporting form will be completed for each event that requires reporting.

Adverse events or SAEs occurring between visits/questionnaires/sample collections will not be recorded or reported as they are not the aim or focus of this project.

15. Monitoring and auditing

The Sponsor or delegate retains the right to audit any study, study site or central facility. In addition, any part of the study may be audited by the funders where applicable.

Onsite monitoring will be performed as per the study monitoring plan. Monitoring will include source data verification. We will check 100% of consent forms and the CI will undertake spot checks on the quality of recorded data.

16. Study committees

We will form a study management group consisting of the CI, PIs, collaborators, grant holders, statisticians and study coordination team. Since this is a pilot, minimal

risk study, we will not have a Data Monitoring Committee or a Trial Steering Committee.

17. Finance and funding

The project is funded by Barts Charity ([name]); grant number MRC0219).

18. Insurance and indemnity

The insurance that Queen Mary University of London has in place provides cover for the design and management of the study as well as "No Fault Compensation" for participants, which provides an indemnity to participants for negligent and non-negligent harm.

19. Dissemination of research findings

We will disseminate findings through conferences and 2-3 open access peer-reviewed manuscripts. We will produce policy briefs and press releases to communicate findings to policymakers, including Public Health England, the Patients Association and non-governmental organisations such as Save The Children, who have a strong focus on national health and education policy. If we find a substantial hidden burden of stunting, we anticipate drafting a Viewpoint for a journal such as the BMJ or Lancet to highlight the issue, as well as dissemination to the press. There is a need for earlier diagnosis of serious underlying medical disorders in children with growth failure, as is evident from the testimonials we have included with this proposal.

We will leverage the support of the Child Growth Foundation, for whom [name] is a medical advisor, to disseminate the results of the automated growth screening algorithm which has enormous national potential. This would require further evaluation in a follow-on grant, and we plan to apply for NIHR funding following the results of our pilot assessment. We will establish a community advisory board with representation from parents, primary care and local education; this will enable us to gain a range of viewpoints on the proposed work and its implications. We will engage parents through letters prior to the start and end of the project, and through an invited parents' evening to disseminate findings. This work synergizes with ongoing work in sub-Saharan Africa, which focuses on stunting as a marker of poverty, and aims to identify solutions to child linear growth failure. We have an ongoing collaboration with the Centre of the Cell at the Blizard Institute to develop a game and app on undernutrition in Africa; we will use

this as an opportunity to also highlight issues related to local undernutrition for the general public.

We will produce policy briefs and press releases to communicate findings to policymakers, including Public Health England, the Patients Association and nongovernmental organisations such as Save The Children, who have a strong focus on national health and education policy.

20. References

¹ Ahmed ML et al. Evaluation of a district growth screening programme: the Oxford Growth Study. *Arch Dis Child* 1993 **69** 361-365.

² Voss LD et al. Poor growth in school entrants as an index of organic disease: the Wessex growth study. *BMJ* 1992 **305** 1400-1402.

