An identification of short stature, faltering growth or delayed development (and subsequent referral for specialist care) could result in distress for children and their families and could lead to stigma. We will include information about stigma and discuss this with caregivers as part of the informed consent procedures. Further, if we identify issues with growth and/or development, children will be referred earlier than would have happened without their involvement in the study. Children will be immediately referred to a paediatric growth or community development clinic and as such will be provided care, support and if appropriate treatment for relevant conditions.

We will be providing vouchers worth £15 for the baseline visit as compensation for time spent during participation in the study. These are not intended as rewards for participation, but we are aware of the possibility of these payments leading to coercion. Research staff will undergo Good Clinical Practice and ethics training and will be careful to avoid coercion in recruitment procedures.

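### Section 14 contradicts itself: related adverse events go to the CI without time limit, yet events between visits, with no exception for related ones, are not recorded.

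*Protocol*

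**What the plan says.** Section 14 considers two kinds of harm. On the first it says: "There is a very low likelihood of physical injury during the growth and development assessments". On the second it says: "There is potential for distress or psychological harm of the child or family member when being informed of abnormal growth or development", and extends this with "or when being referred to the growth clinic". Section 11 (Ethics) makes the same point about identification and referral, which "could result in distress for children and their families and could lead to stigma".

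On timing, section 14 says: "There are two points at which participants will be seen face-to-face". It lists contacts with families of children who warrant referral separately, "which will be in the form of a telephone call and/or letter to the family". Section 9.4 agrees: at each of the three height measurements the algorithm flags the poorest-growing children, and a study team member then telephones the parents.

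Section 14 then gives two recording rules:

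- **Inclusion rule.** "Any AEs that are plausibly related to the study and which are identified by a member of the research team" are to be reported to the CI, assessed for severity and relatedness, and passed on to the JRMO if severe or serious and at least possibly related to study procedures. No time window is attached.
- **Exclusion rule.** "Adverse events or SAEs occurring between visits/questionnaires/sample collections will not be recorded or reported". The reason given is that such events are outside the project's aim. There is no exception for related or serious events.

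**The concern.** The rules are written as though they address different events, but they overlap. An event that is plausibly related, known to the team and arising between visits must be reported under one and must not be recorded under the other. Harm from a referral call or letter falls in that overlap.

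A team member who learns of serious distress after a call could follow either sentence and be compliant. Under the exclusion rule the event would not be assessed by the CI or considered for onward reporting. The pilot's primary endpoint is feasibility and acceptability (section 6.3), and uptake of referral is one of its hypotheses (section 6.1), so harm from notification and referral bears directly on what the study is meant to inform. Section 16 provides no Data Monitoring Committee or Trial Steering Committee, which leaves the CI route as the main safeguard.

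**Working it through.** The check is one of consistency. The protocol gives no figure for this point that could be reproduced, so the provisions are set side by side.

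1. **Where the named harm arises.** Section 14 ties distress to the moment of being informed or referred. Contacts about referral are by telephone and/or letter and are listed apart from the two face-to-face points.

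2. **What the exclusion covers.** It removes events between visits, questionnaires and sample collections. A referral call or letter is, on ordinary reading, none of these.

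3. **How the two rules apply to each kind of event.**
   - Related, at a visit: the inclusion rule requires reporting and the exclusion does not apply. No conflict.
   - Unrelated, between visits: the inclusion rule does not apply and the exclusion says not to record. No conflict.
   - Unrelated, at a visit: neither rule applies. No conflict.
   - Related, identified by the team, between visits: one rule requires reporting and the other forbids recording. **Conflict.**

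   The conflict is confined to the last case, and by steps 1 and 2 a referral-related event belongs there.

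4. **The final measurement.** The algorithm also runs on the school measurement at age 4-5 years (section 9.4). Section 14 treats that measurement as not strictly a study procedure, and section 9.8 ends each child's participation after it. A family first flagged then has no later face-to-face study visit, although an end-of-study caregiver questionnaire follows (Form 19).

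5. **How many families.** Section 10.1 expects 2% of 600 children to be referred: 0.02 × 600 = 12. Sections 9.4 and 8 give 2-3%; at 3% the number would be 0.03 × 600 = 18. These are families receiving a referral contact. They are not counts of distressed families, for which the protocol gives no rate. Families told of developmental concerns would add to them, but the protocol does not estimate that number.

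6. **A sign of carried-over text.** The exclusion mentions sample collections, yet section 9.6 says laboratory investigations are not performed as part of the study. The sentence may therefore not have been written for this design. That is an inference and the contradiction does not depend on it.

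**The case against.** The strongest reply is that section 14 can be read consistently. After a paragraph about related events, a closing sentence justified by the project's aim may mean only that background childhood illness between contacts will not be tracked. Section 14 also calls the referral call a contact, and the person breaking the news is to be a senior, medically trained team member, so distress voiced on that call is identified by someone whom the inclusion rule covers. This reading is reasonable and may be the intended one. The sentence does not say it, however: it has no relatedness condition and expressly includes serious events.

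The second reply is that other capture exists. Section 6.3 plans questionnaires to all caregivers, and section 9.4 says they will be used to evaluate acceptability of screening and referral. The exclusion itself names questionnaires among its contact points. This stands in part: some distress may surface there, but as acceptability data, with no stated link to assessment by the CI.

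A reader might go further and infer that distressed families have no route to the CI, or that the pilot would show no adverse events whatever referral did to families. The documents do not support either. The inclusion rule has no time limit, nothing says that the exclusion overrides it, and events at study visits remain reportable. Developmental results are discussed with caregivers (sections 5.3 and 13.1), and nothing says that this happens only between visits.

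It would also be wrong to call distress the protocol's main foreseeable harm. Section 14 speaks of potential, and section 11 lists identification through sensitive data first.

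**Conclusion.** The contradiction is real and should be resolved. It affects one class of event: plausibly related, known to the team and arising between visits. Taken literally, the exclusion would drop such events, serious ones included, when they follow a referral call or letter. About 12 families would receive such a contact on the 2% figure in section 10.1, or 18 at the upper 3%, assuming 600 children are measured.

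The conclusion assumes that a telephone call or letter is not a visit, questionnaire or sample collection, and that staff apply the exclusion as worded. If they apply the inclusion rule instead, nothing is lost.

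A tempting way to size the point is to take the 60-70% of referred children expected to have no disorder, 12 × 0.60 to 12 × 0.70 = 7.2 to 8.4, as the number of families distressed without a diagnosis. The documents do not support that use. They give no distress rate, and whether a child is later diagnosed has no bearing on whether an event is recorded.

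**What to change.** Reconcile the two rules in section 14:

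- Limit the between-visits exclusion to events not plausibly related to the study.
- State that events plausibly related to notification, referral or developmental feedback are recorded and reported to the CI whenever the team becomes aware of them.
- Remove the reference to sample collections if none are planned.

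The cost is one or two sentences and a few extra event records. No new visit is needed. A fixed collection window, or a separate count of such events beside the referral yield, would be an optional addition; the contradiction can be resolved without either.
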